**Study Population:**

Describe the characteristics of the subject population, including age range, gender, ethnic background and health status. Identify the criteria for inclusion and exclusion.

Provide the following information:

- A description of the subject selection criteria and rationale for selection in terms of the scientific objectives and proposed study design;
- A compelling rationale for proposed exclusion of any sex/gender or racial/ethnic group;
- Justification for the inclusion of vulnerable groups such as children, prisoners, adults with impaired consent capacity, or others who may be vulnerable to coercion or undue influence.

Please consider these resources:

[NIH Diversity Policy](#)

[FDA Diversity Guidance](#) 

Inclusion criteria. Potential participants will be: 1) Patients seen at a clinic within the University of Kentucky Healthcare; 2) 21-60 years of age; 3) male or female gender 4) Able to read, understand and communicate in English; 5) willing to adhere to the general rules of the UK Healthcare; 6) Must fulfill DSM criteria for moderate alcohol use disorder.

Exclusion criteria. Positive pregnancy test for females, traumatic brain injury, history of seizure disorder, history of or current diagnosis of schizophrenia, intracranial metal shrapnel, previous adverse effect with TMS, sub-threshold consistency while performing behavioral tasks, failure to show baseline attentional bias to alcohol versus neutral cues.

**Attachments**

Indicate the targeted/planned enrollment of the following members of minority groups and their subpopulations. Possible demographic sources: [Census Regional Analyst Edition](#), [Kentucky Race/Ethnic Table](#), [Kentucky Population Data](#).

(Please note: The IRB will expect this information to be reported at Continuation Review time for Pre-2019 FDA-regulated Expedited review and Full review applications):

Participant Demographics			
	Cisgender Man 	Cisgender Woman 	TGNB/TGE 
American			
Indian/Alaskan Native:			
Asian:			
Black/African American:			
Latinx:			
Native Hawaiian/Pacific Islander:			
White:			
American Arab/Middle Eastern/North African:			
Indigenous People Around the World:			
More than One Race:			
Unknown or Not Reported:			

If unknown, please explain why:

Indicate the categories of subjects and controls to be included in the study. You may be required to complete additional forms depending on the subject categories which apply to your research. If the study does not involve direct intervention or direct interaction with subjects, (e.g., record-review research, outcomes registries), do not check populations which the research does not specifically target. For example: a large record review of a diverse population may incidentally include a prisoner or an international citizen, but you should not check those categories if the focus of the study has nothing to do with that status.

Check All That Apply (at least one item must be selected)

**ADDITIONAL INFORMATION:**

- Children (individuals under age 18)
- Wards of the State (Children)
- Emancipated Minors
- Students
- College of Medicine Students
- UK Medical Center Residents or House Officers
- Impaired Consent Capacity Adults
- Pregnant Women/Neonates/Fetal Material
- Prisoners
- Non-English Speaking (translated long or short form)
- International Citizens
- Normal Volunteers
- Military Personnel and/or DoD Civilian Employees
- Patients
- Appalachian Population

Please visit the [IRB Survival Handbook](#) for more information on:

- Children/Emancipated Minors
- Students as Subjects
- Prisoners
- Impaired Consent Capacity Adults
- Economically or Educationally Disadvantaged Persons

Other Resources:

- UKMC Residents or House Officers [see [requirement of GME](#)]
- [Non-English Speaking](#) [see also the E-IRB Research Description section on this same topic]
- [International Citizens](#) [DoD SOP may apply]
- [Military Personnel and/or DoD Civilian Employees](#)

**Assessment of the potential recruitment of subjects with impaired consent capacity (or likelihood):**

Check this box if your study does NOT involve direct intervention or direct interaction with subjects (e.g., record-review research, secondary data analysis). If there is no direct intervention/interaction you will not need to answer the impaired consent capacity questions.

Does this study focus on adult subjects with any conditions that present a high *likelihood* of impaired consent capacity or *fluctuations* in consent capacity? (see examples below)

Yes  No

If Yes and you are not filing for exemption certification, go to "[Form T](#)", complete the form, and attach it using the button below.

**Examples of such conditions include:**

- Traumatic brain injury or acquired brain injury
- Severe depressive disorders or Bipolar disorders
- Schizophrenia or other mental disorders that involve serious cognitive disturbances
- Stroke
- Developmental disabilities
- Degenerative dementias
- CNS cancers and other cancers with possible CNS involvement
- Late stage Parkinson's Disease
- Late stage persistent substance dependence
- Ischemic heart disease
- HIV/AIDS
- COPD
- Renal insufficiency
- Diabetes
- Autoimmune or inflammatory disorders
- Chronic non-malignant pain disorders
- Drug effects
- Other acute medical crises

Attachments

## INFORMED CONSENT/ASSENT PROCESS/WAIVER

0 unresolved  
comment(s)

For creating your informed consent attachment(s), please download the most up-to-date version listed in "All Templates" under the APPLICATION LINKS menu on the left, and edit to match your research project.

## Additional Resources:

- [Informed Consent/Assent Website](#)
- [Waiver of Consent vs. Waiver of Signatures](#)
- [Sample Repository/Registry/Bank Consent Template](#)

## Consent/Assent Tips:

- If you have multiple consent documents, be sure to upload each individually (not all in a combined file).
- If another site is serving as the IRB for the project, attach the form as a "Reliance Consent Form" so the document will not receive a UK IRB approval stamp; the reviewing IRB will need to stamp the consent forms.
- Changes to consent documents (e.g., informed consent form, assent form, cover letter, etc...) should be reflected in a 'tracked changes' version and uploaded separately with the Document Type "Highlighted Changes".
- It is very important that only the documents you wish to have approved by the IRB are attached; DELETE OUTDATED FILES -- previously *approved* versions will still be available in Protocol History.
- Attachments that are assigned a Document Type to which an IRB approval stamp applies will be considered the version(s) to be used for enrolling subjects once IRB approval has been issued.

Document Types that do NOT get an IRB approval stamp are:

- "Highlighted Changes",
- "Phone Script", and
- "Reliance Consent Form",
- "Sponsor's Sample Consent Form".

## How to Get the Section Check Mark

1. You must:
  - a) provide a response in the text box below describing how investigators will obtain consent/assent, and
  - b) check the box for at least one of the consent items and/or check mark one of the waivers
2. If applicable attach each corresponding document(s) **as a read-only PDF**.
3. If you no longer need a consent document approved (e.g., closed to enrollment), or, the consent document submitted does not need a stamp for enrolling subjects (e.g., umbrella study, or sub-study), only select "Stamped Consent Doc(s) Not Needed".
4. After making your selection(s) be sure to scroll to the bottom of this section and **SAVE** your work!

## Check All That Apply

Informed Consent Form (and/or Parental Permission Form and/or translated short form)

Assent Form

Cover Letter (for survey/questionnaire research)

Phone Script

Informed Consent/HIPAA Combined Form

Debriefing and/or Permission to Use Data Form

Reliance Consent Form

Sponsor's sample consent form for Dept. of Health and Human Services (DHHS)-approved protocol

Stamped Consent Doc(s) Not Needed

## Attachments

## Informed Consent Process:

Using active voice, in the text box below, describe how investigators will obtain consent/assent. Include:

- the circumstances under which consent will be sought and obtained
- the timing of the consent process (including any waiting period between providing information and obtaining consent)

- who will seek consent
- how you will minimize the possibility of coercion or undue influence
- the method used for documenting consent
- if applicable, who is authorized to provide permission or consent on behalf of the subject
- if applicable, specific instruments or techniques to assess and confirm potential subjects' understanding of the information

Will electronic consent form/process be utilized on-site or remotely for this study?

Yes  No

If yes, in addition to addressing the above bullet points, describe the e-consent method and platform, including any hyperlinks, videos, or enhancements used to convey information, if applicable. Attach a representation of the e-consent with signature fields. For guidance, see the ORI [E-Consent web page](#).

Note: all individuals authorized to obtain informed consent should be designated as such in the E-IRB "Study Personnel" section of this application.

Special considerations may include:

- Obtaining consent/assent for special populations such as children, prisoners, or people with impaired decisional capacity
- *Research Involving Emancipated Individuals*  
If you plan to enroll some or all prospective subjects as emancipated, consult with UK legal counsel **prior to submitting this application to the IRB**. Include research legal counsel's recommendations in the "Additional Information" section as a separate document.
- *Research Involving Non-English Speaking Subjects*  
For information on inclusion of non-English speaking subjects, or subjects from a foreign culture, see IRB Application Instructions for Recruiting Non-English Speaking Participants or Participants from a Foreign Culture.
- *Research Repositories*  
If the purpose of this submission is to establish a research repository describe the informed consent process. For guidance regarding consent issues, process approaches, and sample language see the [Sample Repository/Registry/Bank Consent Template](#).

Informed consent will be obtained after thorough discussion of the research project, what is required of the participant, the risks and benefits of participation in the study, and the procedures that are in place if/when challenges arise. This will be done by the PI, one of the co-investigators or research assistant during the first encounter with the subject, if they fulfill all eligibility criteria and are interested in study participation.

The research project is not connected to the SMART clinic (i.e., a person can be enrolled in the SMART clinic and their participation in the research project does not impact their standing in the SMART clinic and therefore the participation is truly voluntary in nature. If you have questions about the study, you can contact the principal investigator for the study [name] at [contact]. If you have concerns or questions about your rights and/or welfare as a volunteer in this research, you can contact the staff in the Office of Research Integrity at The University of Kentucky at [contact] or toll free at [name]. We will give you a signed copy of this consent form to take with you.

Request for Waiver of Informed Consent Process

If you are requesting IRB approval to waive the requirement for the informed consent process, or to alter some or all of the elements of informed consent, complete, Section 1 and Section 2 below.

Note: The IRB does not approve waiver or alteration of the consent process for greater than minimal risk research, except for planned emergency/acute care research as provided under FDA regulations. Contact ORI for regulations that apply to single emergency use waiver or acute care research waiver [contact]).

#### SECTION 1.

Check the appropriate item:

I am requesting a waiver of the requirement for the informed consent process.

I am requesting an alteration of the informed consent process.

If you checked the box for this item, describe which elements of consent will be altered and/or omitted, and justify the alteration.

#### SECTION 2.

Explain how each condition applies to your research.

a) The research involves no more than minimal risk to the subject.

b) The rights and welfare of subjects will not be adversely affected.

c) The research could not practicably be carried out without the requested waiver or alteration.

d) Whenever possible, the subjects or legally authorized representatives will be provided with additional pertinent information after they have participated in the study.

e) If the research involves using or accessing identifiable private information or identifiable biospecimens, the research could not practicably be carried out without using such information or biospecimens in an identifiable format.

- Private information/specimens are “identifiable” if the investigator may ascertain the identity of the subject or if identifiers are associated with the information (e.g., medical records). This could be any of the [18 HIPAA identifiers](#) including [dates of service](#).
- If not using identifiable private information or identifiable biospecimens, insert N/A below.

If you are requesting IRB approval to waive the requirement for signatures on informed consent forms, **your research activities must fit into one of three regulatory options:**

1. The only record linking the participant and the research would be the consent document, and the principal risk would be potential harm resulting from a breach of confidentiality (e.g., a study that involves participants who use illegal drugs).
2. The research presents no more than minimal risk to the participant and involves no procedures for which written consent is normally required outside of the research context (e.g., a cover letter on a survey, or a phone script).
3. The participant (or legally authorized representative) is a member of a distinct cultural group or community in which signing forms is not the norm, the research presents no more than minimal risk to the subject, and there is an appropriate alternative mechanism for documenting that informed consent was obtained.

Select the option below that best fits your study.

*If the IRB approves a waiver of signatures, participants must still be provided oral or written information about the study. To ensure you include required elements in your consent document, use the **Cover Letter Template** as a guide. There is an [English](#) and a [Spanish](#) version.*

**Option 1**

**Describe how your study meets these criteria:**

- a) The only record linking the participant and the research would be the consent document:
- b) The principal risk would be potential harm resulting from a breach of confidentiality (i.e., a study that involves subjects who use illegal drugs).

Under this option, each participant (or legally authorized representative) must be asked whether (s)he wants to sign a consent document; if the participant agrees to sign a consent document, only an IRB approved version should be used.

**Option 2**

**Describe how your study meets these criteria:**

- a) The research presents no more than minimal risk to the participant:
- b) Involves no procedures for which written consent is normally required outside of the research context (i.e. a cover letter on a survey, or a phone script):

**Option 3**

**Describe how your study meets these criteria:**

- a) The subject (or legally authorized representative) is a member of a distinct cultural group or community in which signing forms is not the norm.
- b) The research presents no more than minimal risk to the subject.
- c) There is an appropriate alternative mechanism for documenting that informed consent was obtained.

## STUDY PERSONNEL

Do you have study personnel who will be assisting with the research?

After selecting 'Yes' or 'No' you must click the 'Save Study Personnel Information' button. [?](#)

Yes  No

## RESEARCH DESCRIPTION

0 unresolved  
comment(s)

You may attach a sponsor's protocol pages in the "Additional Information" section and refer to them where necessary in the Research Description. However, each prompt that applies to your study should contain at least a summary paragraph.

**Pro Tips:**

- Save your work often to avoid losing data.
- Use one of the attachment buttons in this section or under the Additional Information section to include supplemental information with your application. During the document upload process, you will be able to provide a brief description of the attachment.

**Background**

Include a brief review of existing literature in the area of your research. You should identify gaps in knowledge that should be addressed and explain how your research will address those gaps or contribute to existing knowledge in this area. For interventional research, search PubMed and ClinicalTrials.gov for duplicative ongoing and completed trials with same condition and intervention(s).

Alcohol use disorder (AUD) imposes significant financial burden on society globally and nationally. Alcohol use disorder is the leading risk factor for attributable burden of disease among people ages 25 to 49, the second-leading risk factor among ages 10 to 24, and the ninth-leading risk factor among all ages (1). Although pharmacotherapy and behavioral treatments have been approved for AUD, their effects sizes are modest (2). Noninvasive neuromodulation can offer an alternative treatment option for AUD (3). Transcranial magnetic stimulation (TMS) is a method of noninvasive neuromodulation that utilizes a magnetic field to focal electrical current in the brain (4). When these electrical currents are focused on specific brain regions, pertinent to the neurobiology of AUD it leads to modulation of behavior and plausibly decrease in alcohol craving and use (5).

Previous TMS studies have used heterogenous parameters, including frequencies ranging from 1 Hz to 20 Hz (3, 6-9). Regions targeted by these studies encompassed ventromedial prefrontal cortex, left dorsolateral prefrontal cortex (left dlPFC) and right dorsolateral prefrontal cortex (3). Two studies used a TMS paradigm with greater efficiency than other routine TMS paradigms, called continuous theta burst stimulation (6, 7). These studies delivered 3600 pulses of cTBS to the left frontal pole/ventromedial prefrontal cortex and showed significant reduction in alcohol cue reactivity and corroborative changes in both resting state and task based functional connectivity (6, 7). Of these two studies, one was notable in comparing active cTBS (3600 pulses per session, one session every day for ten days over two weeks) versus sham cTBS. This study showed that real cTBS led to a significantly greater reduction in brain reactivity to alcohol cues, specifically a reduction in MPFC-striatum and MPFC-insula connectivity 2 and 3 months after TBS treatment (6).

A deep TMS study that compared dTMS (15 sessions, five sessions every week for three weeks) to sham dTMS using an H7 coil (targeting medial prefrontal and anterior cingulate cortices) (9). This study showed decreased craving after treatment and percentage of heavy drinking days (9) in the active versus sham control group. Active dTMS was associated with decreased resting-state functional connectivity of the dorsal anterior cingulate cortex with the caudate nucleus and decreased connectivity of the medial prefrontal cortex to the subgenual anterior cingulate cortex (9).

No study has done multiple sessions of cTBS in a single day. In addition, no study has previously delivered cTBS to the left dlPFC, to modulate executive control. Previous studies delivered cTBS to the left frontal pole or ventromedial prefrontal cortex to modulate cue-reactivity.

## Objectives

List your research objectives. Please include a summary of intended research objectives in the box below.

To demonstrate whether two sessions of continuous TBS (cTBS) decreases attentional bias for alcohol cues, alcohol craving and changes resting state functional connectivity in people with alcohol use disorder (AUD) compared to two sessions of sham cTBS. We hypothesize 2 sessions of cTBS to the left dorsolateral prefrontal cortex (L. dlPFC) will significantly decrease attentional bias for alcohol cues, alcohol craving and change resting state functional connectivity in a population of people with AUD compared to sham cTBS.

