On day two of the study all study participants will receive active stimulation which is two sessions of continuous theta burst stimulation (cTBS) to the left dorsolateral prefrontal cortex. Both sessions will be separated by 50 minutes. Participants will perform the alcohol craving scale, AUDIT-C and attentional bias for alcohol cues before and after the two cTBS sessions. The same sequence of events will occur on day three of the study, but all participants will receive sham cTBS. We will acquire functional MRI (fMRI) scan on both study days 2 and 3, after the active cTBS sessions and sham cTBS session respectively. Study days 2 and 3 will be separated by a week.

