**Research Procedures**

Describe how the research will be conducted.

- What experience will study participants have?
- What will study participants be expected to do?
- How long will the study last?
- Outline the schedule and timing of study procedures.
- Provide visit-by-visit listing of all procedures that will take place.
- Identify all procedures that will be carried out with each group of participants.
- Describe deception and debrief procedures if deception is involved.

Differentiate between procedures that involve standard/routine clinical care and those that will be performed specifically for this research project. List medications that are explicitly forbidden or permitted during study participation.

On day one of the study, following informed consent, we will perform baseline assessments including breath alcohol level, alcohol craving questionnaire, alcohol attentional bias tasks using eye tracker, and collection of baseline demographics. All of these baseline assessments will take a total of three hours. We will evaluate for any contraindications for MRI using the MRI checklist (attached). We will also obtain resting and active motor threshold from the first dorsal interosseous (FDI) muscle. Following this subjects will be transported to Magnetic Resonance Imaging and Spectroscopy Center (MRISC), affiliated with University of Kentucky for collection of their baseline MRI brain scan that will last thirty minutes. A study team member will escort them to the MRISC and will be with them when the scan is obtained.

On the second day, subjects will receive two sessions of active cTBS. Sessions will be the same in dosing and will be delivered at an interval of fifty minutes. Each session will last five minutes regardless of it being cTBS or sham cTBS. Active cTBS sessions will be delivered 120% resting motor threshold (RMT) to the left dorsolateral prefrontal cortex using a figure 8 coil and MagVenture MagPro x100 device (MagVenture A/S, Denmark), with TMS coil position stabilized using BrainSight (Rogue Solutions, Montreal, Canada). Subjects will also perform a host of other tasks as shown in figure 1 before and after the two cTBS sessions. At the end of the cTBS sessions and tasks, post session MRI brain scan will be collected at MRISC.

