## Data Collection & Research Materials

In this section, please provide the following:

- Describe all sources or methods for obtaining research materials about or from living individuals (such as specimens, records, surveys, interviews, participant observation, etc.), and explain why this information is needed to conduct the study.
- For each source or method described, please list or attach all data to be collected (such as genetic information, interview scripts, survey tools, data collection forms for existing data, etc.).
- If you will conduct a record or chart review, list the beginning and end dates of the records you will view.

Motor Threshold  
 Eye tracking  
 AUDIT- C  
 FTND  
 MAST  
 DAST  
 History if any of traumatic brain injury or loss of consciousness.  
 Alcohol craving scale  
 TMS Side effects scale  
 Treatment acceptability questionnaire (TAQ)  
 Resting state functional magnetic resonance imaging (fMRI)  
 Heart rate data using Fitbit

Neuroimaging data will be acquired on a Siemens 3-Tesla (3T) PRISMA scanner at the Magnetic Resonance Imaging and Spectroscopy Center (MRISC), situated close to Markey Cancer Center. A high-resolution (1 cubic millimeter voxels) T1- weighted MP-RAGE structural image will be acquired for each subject. Functional images will be acquired using echo-planar imaging. Hyper-angulated volumes will be acquired with 37 ascending and interleaved slices at an angle 30-degrees to the anterior-posterior commissure to prevent OFC washout. Additional parameters will be similar to those used in other approved neuroimaging protocols in our lab (e.g., a repetition time (TR) of 2 seconds, echo time (TE) of 25 ms, a flip angle of 90 degrees, and functional voxels of size 3.4mm x 3.4mm x 4.0mm). Image preprocessing will be performed in Conn Toolbox.

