### Statistical analysis plan

We will calculate the mean and standard deviation values for PACS scores and alcohol cue attentional bias values for two time points (baseline and following the second session). This will be done across both cTBS and sham cTBS sessions. We will compare changes in these outcome measures across cTBS and sham cTBS sessions using t-tests.

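### Must the SAP be changed because it gives no connectivity test, no ranking of outcomes and no visit for baseline?

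*Combined protocol and SAP*

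**What the plan says.** The Objectives name three effects versus sham in one sentence: active stimulation "will significantly decrease attentional bias for alcohol cues, alcohol craving and change resting state functional connectivity in a population of people with AUD". The outcomes are joined by a conjunction and are not ranked.

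The Statistical analysis plan is three sentences long. It summarises craving (PACS) and "alcohol cue attentional bias values for two time points (baseline and following the second session"), does so for both the active and the sham sessions, and ends: "We will compare changes in these outcome measures across cTBS and sham cTBS sessions using t-tests". It gives no significance level, sidedness, pairing, multiplicity rule or success criterion, and it does not mention imaging.

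On imaging, the Data Collection section gives scanner settings and then "Image preprocessing will be performed in Conn Toolbox". The Study Design schedules a baseline scan on Day 1 and adds: "We will acquire functional MRI (fMRI) scan on both study days 2 and 3, after the active cTBS sessions and sham cTBS session respectively". Research Procedures agrees for Day 2: "At the end of the cTBS sessions and tasks, post session MRI brain scan will be collected at MRISC". No scan is listed before stimulation on Day 2 or Day 3.

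Two places bear on baseline for the behavioural outcomes. Research Procedures says that on Day 1 "we will perform baseline assessments including breath alcohol level, alcohol craving questionnaire, alcohol attentional bias tasks using eye tracker" will be done. For Day 2 the Study Design says "Participants will perform the alcohol craving scale, AUDIT-C and attentional bias for alcohol cues before and after the two cTBS sessions", and it repeats the sequence on Day 3 with sham.

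**The concern.** A hypothesis that speaks of a significant effect on three outcomes implies three tests, and the plan supplies two. Followed to the letter, the plan would leave the scans without an inferential result, although the Background presents connectivity changes as important findings of earlier stimulation studies.

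The other omissions seem to compound this. Without a ranked outcome or success rule, either of two results could be presented as the trial's finding. If baseline could mean Day 1 or the same day, the tested quantity itself is open. The study is closing with only data analysis left, so choices made now could follow the results. At stake would be an untested objective, a false-positive rate above the nominal level, and an estimate whose definition depends on an unwritten choice.

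**Working it through.** **Inputs.** Planned size: 30, within participant (Study Design). Enrolled: 4 previously reported + 4 new = 8 (Subject Info To-Date). The plan gives no level, power, effect size or SD with its 30, so there is no figure of its own to reproduce. Assumed for illustration: two-sided 0.05 per test, paired t-tests, and all enrolled participants completing both stimulation days.

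**1. Does the planned comparison carry over to connectivity?** Let D be the Day 1 scan, A the scan after active stimulation on Day 2 and S the scan after sham on Day 3. All three are scheduled. The difference between the two changes is

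(A − D) − (S − D) = A − S.

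The shared baseline cancels, leaving a paired post-active versus post-sham contrast. The absence of a same-day pre-stimulation scan limits what the contrast means, but does not prevent the test. The seed region, threshold and correction method remain unwritten.

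**2. Which baseline applies to PACS and attentional bias?** With pre-stimulation measures a (Day 2) and s (Day 3), a same-day baseline gives

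(A − a) − (S − s) = (A − S) + (s − a),

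so the two readings do differ. Their precision can differ in either direction. With unit SDs, within-day correlation rw and between-day correlation rb (all assumed), the contrast SD is √(2 − 2rb) for a Day 1 baseline and √(4 − 4rw) for a same-day baseline:

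| rw | rb | Day 1 baseline | Same-day baseline |
|---|---|---|---|
| 0.5 | 0.5 | 1.00 | 1.41 |
| 0.8 | 0.5 | 1.00 | 0.89 |

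The readings are not equally supported, however. The SAP takes its two time points within both the active and the sham sessions, which matches the before-and-after measurements scheduled on Days 2 and 3. The Day 1 reading is weaker for PACS: the Study Design's Day 1 list has no craving measure, and only Research Procedures adds one. An analyst reading both sections would use the same-day measure.

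**3. How large is the multiplicity risk?** If success on either of two independent tests counted, the chance of at least one false positive would be 1 − 0.95² = 9.75%. Simulation with correlated outcomes gives about 9% at correlation 0.5 and about 8% at 0.8, for 8 or 30 participants. If every outcome must succeed, there is no inflation. The Objectives join the outcomes with a conjunction, so the reading that produces inflation is the less natural one.

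**4. What would a hierarchy buy at the enrolled size?** Differences are in SDs of the paired difference. The half-width is t(0.975, n − 1)/√n; for n = 8 this is 2.365/2.828 = 0.84.

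| n | Detectable at 80% power, level 0.05 | Same, level 0.025 | 95% interval half-width |
|---|---|---|---|
| 30 | 0.53 | 0.59 | ±0.37 |
| 8 | 1.16 | 1.34 | ±0.84 |

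At 8 participants, only a very large effect is detectable with or without an adjustment. The estimates and their intervals will carry the information.

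**5. Is anything ranked elsewhere?** The Attentional Bias task section calls mean fixation time its main dependent variable. That selects a measure within the eye-tracking task. It does not place attentional bias above craving, and it does not remove the silence on ranking.

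**The case for a change.** The strongest case for a change is that the missing connectivity test is a fact of the text and needs no assumed number. Imaging analysis offers wide freedom in seed, model and threshold, and naming the preprocessing software restricts none of it. The investigator and research assistant know which intervention was given, and the continuing-review form already reports reduced craving among participants. A short dated addition would be cheap and would remove the suspicion that emphasis followed results.

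Part of this stands. Connectivity has no written model, and a connectivity result from this trial could only be read as exploratory. The silence on level, pairing and ranking is also real.

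The rest is weaker. Knowing the intervention is not the same as having seen an outcome contrast; with active always first, anyone holding the protocol knows the labels. The remark about craving appears under benefits, with no PACS score and no comparison with sham, so it does not show that outcomes were analysed. The specific additions one might make, such as attentional bias first or a seed at the stimulated site, are choices the documents do not force: craving first would be equally valid if chosen blind, and the Background reports connectivity of medial prefrontal and cingulate regions. Nor would any of them cure the larger difficulty. The fixed active-then-sham order confounds every comparison with time and carry-over, whichever outcome is ranked first.

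**Conclusion.** No change to the plan follows. What is missing is detail: a connectivity model, a significance level, the word paired, a ranking and a visit label. The within-participant design implies pairing, the session wording points to the same-day baseline, and the scan schedule leads to the post-active versus post-sham contrast. The size is one of three objectives without a written test, plus an error rate of about 8% to 10% that applies only under an assumed two-sided 0.05 level and an either-outcome rule. With 8 enrolled, if all completed both stimulation days, the 95% interval is about ±0.84 SD and a confirmatory claim is out of practical reach under any ranking. The point would be more serious if the documents stated an either-outcome success rule, or showed that the outcome to be emphasised was chosen after its results were seen. They do neither.
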